5.4 PRIMARY SAFETY ENDPOINTS

Treatment-emergent adverse events (TEAEs) and Treatment-emergent Serious Adverse Events (SAEs).

5.5 SECONDARY SAFETY ENDPOINTS

Secondary endpoints include the following:

- Proportion of subjects with Hb >11.0, Hb >12.0, >13.0, or >14.0 g/dL.
- Proportion of subjects with Hb <7.0, <8.0, <9.0, or <10.0 g/dL.
- Proportion of subjects with Hb increase >1.0 g/dL within any 2-week interval or >2.0 g/dL within any 4-week interval.

5.6 OTHER SAFETY ENDPOINTS

Safety will also be evaluated by the following assessments:

- Laboratory test results
- Vital signs

6. STATISTICAL METHODOLOGY AND ANALYSES

6.1 GENERAL CONSIDERATIONS

Data collected throughout the study will be summarized using descriptive statistics and listed in by-subject listings. Continuous variables will be summarized using number of subjects with data, mean, standard deviation (SD), median, minimum, and maximum. For categorical variables, the number and percentage of subjects in each category will be tabulated. Summaries will be provided by treatment group and for vadadustat treatment groups combined within appropriate analysis populations, and by time point/time period, as appropriate.

For Hb, Baseline will be calculated as the average of the last 2 central laboratory Hb measurements of samples taken at or prior to the first dose. For blood pressure, baseline will be calculated as the average of the blood pressure within same visit, and then select

the last available results on or prior to the first dose. For other parameters, unless otherwise specified, Baseline will be defined as the last available value prior to the first dose of study medication.

The primary efficacy endpoint as well as the secondary and all other efficacy endpoints will be summarized using descriptive statistics by treatment group, and by analysis visit and/or analysis period as appropriate. Mean values of Hb and selected other efficacy parameters will be plotted across analysis visits/periods by treatment group.

Hb values will be assessed through the central laboratory for dose adjustments, efficacy, and safety evaluations.

If the central laboratory uses assays that have lower limits of detection (LLD), all laboratory results below the LLD will be imputed with the LLD. Results reported as greater than a value (i.e., “> value”) will be imputed as 1.5 x that value.

Mircera will be converted to IV epoetin equivalent unit per kilogram per week (U/kg/week) as 1:220. The conversion has been derived from published literature ([Paganini, 1995](#); [Kaufman1998](#)[Levin, 2008](#)[Wright2015](#)) and input from clinical experts.

Study days are defined as follows:

Study Day = [Event date – First dosing date + 1], if on or after first dosing date
[Event date – First dosing date], if before first dosing date.

Note that with the definition above, days of “0” will not be used. As such, the study day can be interpreted as the number of days before or after first day of dosing. Event date refers to the date associated with the result being summarized. In some cases, this is the date of an assessment or measurement; in other cases, this is the onset date of an adverse or outcome event.

If the subject numbers, combined over two treatment groups, in one of the strata are less than 30, the strata will be combined with the next large strata for efficacy and safety analyses.

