7.1.2 Dosing and Administration

The aim is to achieve and maintain Hb levels within the target range of 10.0 to 11.0 g/dL inclusive, while targeting the middle of the range and minimizing excursions outside the target range.

Dosing will be initiated at Baseline and the first dose of vadadustat will be administered at the hemodialysis unit after other Baseline procedures have been completed. Thereafter, vadadustat is anticipated to be administered at the hemodialysis unit. Subjects may take vadadustat with or without food and will be instructed to swallow the tablet(s) whole. Subjects are to take vadadustat at roughly the same time each day.

Mircera will be administered IV at the hemodialysis unit based on according to the dialysis center's protocol.

Note: For all subjects, it is recommended that no additional ESA doses will be administered after SV2 after the subject has met all eligibility criteria and before Baseline. For all subjects, it is required that a minimum of 14 days be observed between the last dose of Mircera and the

Baseline visit. If an ESA other than Mircera was administered during the Screening period, the subject will be a screen failure.

After discussion with the Medical Monitor, screening may be extended for an additional 2 to 4 weeks based on subject's Hb level or Hb trajectory or based on timing of last Mircera dose given during Screening and the Baseline visit.

For subjects who are randomized to the Mircera treatment arm, the initial dosing regimen in the study (starting from Baseline) will be according to the dialysis center's protocol. The timing of randomization should align with next anticipated dose of Mircera.

Study Drug Guidelines for Dose Adjustment

Dose adjustments will be guided by central laboratory Hb concentrations throughout the study to determine if vadadustat or Mircera doses will be adjusted, interrupted, or maintained. Mircera dosing will be based on standard of care laboratory measures according to the dialysis center's protocol.

Guidelines for vadadustat dose adjustment are as follows (see [Appendix 1](#)):

- Dose adjustments are based on the Investigator's clinical discretion, incorporating the protocol guidance below as well as the subject's current Hb level, trajectory, and variability; symptoms; CV risk; and other features of his/her clinical condition(s).

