10.5 Statistical Analyses

10.5.1 General Considerations

Data collected throughout the study will be summarized using descriptive statistics and listed in by-subject listings. Continuous variables will be summarized using number of subjects with data,

mean, standard deviation, median, minimum, and maximum. For categorical variables, the number and percentage of subjects in each category will be tabulated. Summaries will be provided by treatment group within appropriate analysis populations (as defined in [Section 10.3](#)) and by time point/time period, as appropriate.

For Hb, Baseline will be calculated as the average of the last 2 central laboratory Hb measurements of samples taken at or prior to the date of first dose. For other parameters, unless otherwise specified, Baseline will be defined as the last available value prior to the first dose of study medication.

The primary efficacy endpoint as well as the secondary and all other efficacy endpoints will be summarized using descriptive statistics by treatment group, as well as by study visit and/or analysis period as appropriate. Mean values of Hb as well as selected other efficacy parameters will be plotted across study visits/periods by treatment group.

Hb values will be assessed through the central laboratory for dose adjustments, efficacy and safety evaluations.

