6.2 VISIT AND ANALYSIS TIME PERIOD CLASSIFICATION

All assessments will be mapped to the corresponding analysis visit (i.e., target week) based on study day, including unscheduled visits. [Table 1](#) is a general window for each visit based on the protocol. [Table 2](#) will be applied for less frequent assessments such as

[REDACTED] C-Reactive Protein (CRP), Complete Blood Count (CBC) with differential, Serum Chemistry, Lipid Panel, Reticulocyte count, Biomarkers, Erythropoietin and Dialysis Adequacy. All other assessments will apply to the analysis window from Table 1.

If more than one Hb assessment is available in a post-baseline analysis period (i.e., PEP or SEP), then all results will be used to calculate the average of Hb. But if more than one record is available in same day, the last assessment (i.e., at most one record per day) will

be used to calculate the average. For other assessments, if more than one assessment is available in each window, the assessment which is closest to the target day will be used for analysis. If the assessments are equally close, the last assessment will be used.

Table 1. Classification of Assessments at Every Visit (General)

Analysis Time Period	Visit	Target Day	Analysis Window
Baseline	Screening Visit 1	-	-
	Screening Visit 2	-	-
Week 2-6	Baseline	Day 1	<=Day 1 (prior to first dose) ^a
	Week 2	Day 14	Day 1 (post dose) – 21
	Week 4	Day 28	Day 22 – 35
Week 8-16	Week 6	Day 42	Day 36 – 49
	Week 8	Day 56	Day 50 – 70
	Week 12	Day 84	Day 71 – 98
Primary Efficacy Period (PEP) (Weeks 20-26)	Week 16	Day 112	Day 99 – 126
	Week 20	Day 140	Day 127 – 154
	Week 24	Day 168	Day 155 – 175
Week 30-42	Week 26	Day 182	Day 176 – 196
	Week 30	Day 210	Day 197 – 224
	Week 34	Day 238	Day 225 – 252
	Week 38	Day 266	Day 253 – 280
Secondary Efficacy Period (SEP) (Weeks 46-52)	Week 42	Day 294	Day 281 – 308
	Week 46	Day 322	Day 309 – 336
	Week 50	Day 350	Day 337 – 357
Safety Follow-up ^b	Week 52	Day 364	Day 358 – 378 or ET/EOT assessment date + 15 days
	Follow-up	ET/EOT assessment date + 28 days	>= ET/EOT assessment date + 15 days

^a If patient has no first dose date, day 1 will be the randomization date.

^b for Vital Sign, Dialysis Access Type, and Therapeutic Phlebotomy

Table 2. Classification of Assessments for Selected Assessment

Analysis Time Period	Visit	Target Day	Analysis Window
Baseline	Screening Visit 1	-	-
	Screening Visit 2	-	-
	Baseline	Day 1	<=Day 1 (prior to first dose) ^a
Week 2-6	Week 4	Day 28	Day 1 (post dose) – 49

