6.12.1 Adverse Events

A treatment-emergent adverse event (TEAE) is one that begins or worsens after treatment initiation. TEAEs will be summarized using the number and percentage of subjects with TEAEs for all subjects in the safety population.

All AEs will be coded by MedDRA. The MedDRA version used for reporting this study will be described in a footnote on AE related outputs. TEAEs will be summarized by SOC and PT for each treatment group. All TEAE summaries will provide the number of subjects reporting at least 1 TEAE. TEAE summaries will be ordered by decreasing pooled percentage for SOC, and PT within SOC.

An overall summary table will show number of subjects with at least 1 of each of the following:

- TEAE
- Drug-related TEAE
- Severe TEAE
- Treatment-emergent SAE
- Drug-related treatment-emergent SAE
- TEAE leading to withdrawal of study drug
- Drug-related TEAE leading to withdrawal of study drug
- Fatal TEAE
- All Deaths: Any deaths reported during the study no matter whether deaths are caused by TEAEs

Summaries by SOC and PT will be provided for the following types of TEAEs:

- TEAE
- TEAE by severity
- Drug-related TEAEs (including all categories for relationship to study medication other than “Unrelated”, as determined by the investigator)
- Treatment-emergent serious adverse event (SAE)

-
- Drug-related treatment-emergent SAE
 - TEAEs leading to withdrawal of study drug
 - Drug-related TEAE leading to withdrawal of study drug
 - Fatal TEAE
 - Adverse events of special interest (AESI) listed on [Appendix E](#)

A summary by treatment group and PT will be presented for TEAEs reported by at least 5% of subjects in either treatment group.

TEAEs will be summarized by 1) worst severity, and 2) worst causality by SOC and PT. For each subject and each PT, the worst severity recorded will be used in the by-severity summaries. Similarly, the worst causality (most related to treatment) attributed will be used in the by-causality summaries. If severity or causality is missing, data will be imputed to the worst category.

Treatment-emergent SAEs and deaths will be summarized by treatment group and overall, including the number and percentage for subject with Treatment-emergent SAEs, number of deaths (all causes, resulting from adverse events). Summary by SOC and PT will include subjects affected by Treatment-emergent SAEs, occurrence (all, causally related to treatment), number of death (all causes), and deaths causally related to treatment.

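### Anchoring Baseline Hb, Day 1 and the efficacy windows to the first dose leaves the Mircera arm open to post-randomization values if its first on-study dose is late or held

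*SAP*

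**What the plan says.** SAP 6.1 defines the Hb anchor: "Baseline will be calculated as the average of the last 2 central laboratory Hb measurements of samples taken at or prior to the first dose". Protocol 10.5.1 has the same rule by date: "measurements of samples taken at or prior to the date of first dose". SAP 6.1 also counts study days from the first dosing date, so that "the study day can be interpreted as the number of days before or after first day of dosing". SAP 6.2 carries this into the analysis periods: "All assessments will be mapped to the corresponding analysis visit (i.e., target week) based on study day, including unscheduled visits". Under its Table 1 the primary efficacy period (PEP) is Days 127–196 and the secondary efficacy period (SEP) is Days 309–378. The randomization date appears only as a fallback: "If patient has no first dose date, day 1 will be the randomization date".

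On the start of treatment, Protocol 7.1.2 initiates dosing at Baseline, and "the first dose of vadadustat will be administered at the hemodialysis unit after other Baseline procedures have been completed". For the control arm it says that the on-study regimen starts from Baseline and follows the dialysis center's protocol, and adds: "The timing of randomization should align with next anticipated dose of Mircera". At least 14 days must separate the last Mircera dose from the Baseline visit, and screening may be extended by 2 to 4 weeks, among other reasons because of Mircera timing. The Schedule of Activities marks Mircera dosing at Baseline.

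**The concern.** For vadadustat, first dose and Baseline visit coincide. For Mircera they coincide only if alignment works. Alignment is worded as a recommendation with no tolerance in days, the dose follows local practice, and Protocol 7.1.2 lets Hb results decide whether doses are adjusted, interrupted or maintained. A first control dose could therefore be held for a reason related to Hb itself. The SAP has no rule for a dosed subject whose first dose is late.

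In that case Hb values taken after randomization count as Baseline. In the primary ANCOVA they enter both the change score and the Baseline covariate, in one arm only. The same lag moves that arm's visits relative to the evaluation windows. This sits badly with SAP 6.11.1, which sets a treatment-policy comparison of assignment in all randomized subjects, and with SAP 3.5, which relies on an identical visit schedule across arms to limit bias.

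**Working it through.** **The plan's own figure.** Protocol 10.2 and SAP 3.3 assume SD 1.2 g/dL, margin −0.75, true difference 0, 150 per arm and 30% dropout, and state power above 90%. Evaluable per arm: 150 × 0.7 = 105.
- One dose arm against Mircera: SE = 1.2 × √(1/105 + 1/105) = 0.166; 0.75/0.166 − 1.96 = 2.57; power 99.5%.
- Combined arms, 210 against 105 (the SAP 6.11.2 contrast): SE = 1.2 × √(1/105 + 1/210) = 0.143; 0.75/0.143 − 1.96 = 3.27; power 99.9%.

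The stated figure is confirmed and does not depend on the anchor.

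**Mapping visits through SAP Table 1.** Let L be the days from the Baseline visit to the first on-study Mircera dose. An on-time visit at week w has study day 7w − L + 1.

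| L (days) | Hb values forming Baseline | Wk 20 | Wk 24 | Wk 26 | Wk 30 | Visits in PEP | Wk 46 |
|---|---|---|---|---|---|---|---|
| 0 | last 2 up to the Baseline visit | 141 | 169 | 183 | 211 | 20, 24, 26 | 323, in SEP |
| 14 | Weeks 0 and 2 | 127 | 155 | 169 | 197 | 20, 24, 26 | 309, in SEP |
| 15 | Weeks 0 and 2 | 126 | 154 | 168 | 196 | 24, 26, 30 | 308, out |
| 28 | Weeks 2 and 4 | 113 | 141 | 155 | 183 | 24, 26, 30 | 295, out |

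When Week 46 drops out, no later treatment visit replaces it. SAP 6.11.2 also limits the primary analysis to data up to the scheduled Week 26 visit. If that means the nominal visit, Week 30 is cut off and only Weeks 24 and 26 remain.

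**Early visits.** A Week 2 visit 3 days early enters Baseline from L = 11 (14 − 3), and a Week 4 visit 3 days early from L = 25. A Week 20 visit that is 3 or 5 days early leaves the PEP from L = 12 or L = 10. Below about 10 days nothing changes for scheduled visits. An unscheduled central Hb before the first dose could still enter Baseline.

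**How long a lag is plausible.** The dosing interval is not stated and is assumed here. With 4-weekly dosing and the 14-day minimum gap, misalignment alone gives at most about 28 − 14 = 14 days; with 2-weekly dosing, about 14 − 14 = 0. A 28-day lag means at least 14 + 28 = 42 days without Mircera, so in practice a held or missed dose.

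**Size of the Baseline effect.** The inputs are assumptions, because the documents give none: 10–30% of controls delayed, Hb drift of 0.3–0.5 g/dL before the first dose, and an ANCOVA slope of follow-up on Baseline Hb of 0.3–0.5.
- Shift in the Mircera mean Baseline = fraction × drift: 0.10 × 0.3 = 0.03 to 0.30 × 0.5 = 0.15 g/dL.
- Shift in the adjusted difference = slope × Baseline shift: 0.3 × 0.03 = 0.009 to 0.5 × 0.15 = 0.075 g/dL.
- If only one of the two Baseline values is affected, halve both: 0.0045 to 0.0375 g/dL in the adjusted difference.

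**Direction.** If control Hb falls while waiting, the shift counts against vadadustat. At the top of the range, combined power is (0.75 − 0.075)/0.143 − 1.96 = 2.75, or 99.7%. If control Hb rises, the shift favors vadadustat. At a true difference exactly at the margin, the one-sided error goes from 2.5% to 7.5% for a shift of 0.075 and to 4.5% for 0.0375. These figures cover the Baseline route only, not the moved window.

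**The case against.** The strongest reply is that the protocol does not plan a later start for Mircera. A reader of the SAP rule alone might infer that vadadustat starts at Baseline by design and Mircera at some later center-scheduled date. The documents do not support that: the control regimen starts from Baseline, the Schedule of Activities marks it there, randomization is meant to meet the next dose, and screening can be extended to bring this about. That stands, so the weakness is conditional on alignment failing or a dose being held.

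It also stands that ordinary misalignment does little. A 14-day lag leaves the on-time PEP visits unchanged and affects one of two Baseline values. A moved window needs 15 days or more with on-time visits.

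A reader might further infer a systematic bias of known sign, or lost control-arm adverse events. Neither frequency nor direction of delay is in the documents. As to adverse events, SAP 6.12.1 says that "A treatment-emergent adverse event (TEAE) is one that begins or worsens after treatment initiation", but it also lists every event before first dose, so these stay visible. Where to start the safety period is a separate choice that this point does not need.

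What the reply does not remove is the missing rule: alignment is not mandatory, and a dosed subject with a late first dose has no randomization-date safeguard.

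**Conclusion.** The point holds as a conditional weakness in the efficacy derivations. If the first on-study Mircera dose is late or held, the control arm alone gets post-randomization Hb in its Baseline (one value from 14 days, both from 28, with on-time visits) and altered evaluation periods from 15 days. Under the stated assumptions the adjusted difference moves about 0.01–0.08 g/dL, or about half that with one Baseline value affected. That is small against the 0.75 margin, can take either sign, and does not threaten power. The delayed fraction, the drift, the slope and the Mircera interval are all assumed, so the size is illustrative. The correction is worth making because it is free: if alignment was perfect the results are identical, and if not, a post-randomization covariate is removed from the primary analysis.

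**What to change.** In SAP 6.1 and 6.2, for efficacy analyses:
- set Day 1 to the randomization/Baseline-visit date in all arms;
- define Baseline Hb as the average of the last 2 central values on or before that date and before any on-study dose.

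Keep the first-dose anchor for exposure and safety summaries, and report the randomization-to-first-dose lag by arm so that readers can see whether alignment worked.

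The cost is SAP wording, one derivation change and one descriptive summary. No new data are needed, and vadadustat subjects dosed at the Baseline visit are unaffected. Protocol 10.5.1 need not be amended, because SAP Section 1 says that the SAP prevails where the two differ; the change should be recorded in SAP Section 7. Nothing here alters how Mircera or vadadustat is given.

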6.2 VISIT AND ANALYSIS TIME PERIOD CLASSIFICATION

All assessments will be mapped to the corresponding analysis visit (i.e., target week) based on study day, including unscheduled visits. [Table 1](#) is a general window for each visit based on the protocol. [Table 2](#) will be applied for less frequent assessments such as

[REDACTED] C-Reactive Protein (CRP), Complete Blood Count (CBC) with differential, Serum Chemistry, Lipid Panel, Reticulocyte count, Biomarkers, Erythropoietin and Dialysis Adequacy. All other assessments will apply to the analysis window from Table 1.

If more than one Hb assessment is available in a post-baseline analysis period (i.e., PEP or SEP), then all results will be used to calculate the average of Hb. But if more than one record is available in same day, the last assessment (i.e., at most one record per day) will

be used to calculate the average. For other assessments, if more than one assessment is available in each window, the assessment which is closest to the target day will be used for analysis. If the assessments are equally close, the last assessment will be used.

Table 1. Classification of Assessments at Every Visit (General)

Analysis Time Period	Visit	Target Day	Analysis Window
Baseline	Screening Visit 1	-	-
	Screening Visit 2	-	-
Week 2-6	Baseline	Day 1	<=Day 1 (prior to first dose) ^a
	Week 2	Day 14	Day 1 (post dose) – 21
	Week 4	Day 28	Day 22 – 35
Week 8-16	Week 6	Day 42	Day 36 – 49
	Week 8	Day 56	Day 50 – 70
	Week 12	Day 84	Day 71 – 98
Primary Efficacy Period (PEP) (Weeks 20-26)	Week 16	Day 112	Day 99 – 126
	Week 20	Day 140	Day 127 – 154
	Week 24	Day 168	Day 155 – 175
Week 30-42	Week 26	Day 182	Day 176 – 196
	Week 30	Day 210	Day 197 – 224
	Week 34	Day 238	Day 225 – 252
	Week 38	Day 266	Day 253 – 280
Secondary Efficacy Period (SEP) (Weeks 46-52)	Week 42	Day 294	Day 281 – 308
	Week 46	Day 322	Day 309 – 336
	Week 50	Day 350	Day 337 – 357
Safety Follow-up ^b	Week 52	Day 364	Day 358 – 378 or ET/EOT assessment date + 15 days
	Follow-up	ET/EOT assessment date + 28 days	>= ET/EOT assessment date + 15 days

^a If patient has no first dose date, day 1 will be the randomization date.

^b for Vital Sign, Dialysis Access Type, and Therapeutic Phlebotomy

Table 2. Classification of Assessments for Selected Assessment

Analysis Time Period	Visit	Target Day	Analysis Window
Baseline	Screening Visit 1	-	-
	Screening Visit 2	-	-
	Baseline	Day 1	<=Day 1 (prior to first dose) ^a
Week 2-6	Week 4	Day 28	Day 1 (post dose) – 49
Week 8-16	Week 12	Day 84	Day 50 – 126
Primary Efficacy Period (PEP) (Weeks 20-26)	Week 26	Day 182	Day 127 – 196
Secondary Efficacy Period (SEP) (Weeks 46-52)	Week 52	Day 364	Day 309 – 378 or ET/EOT assessment date + 15 days

^a If patient has no first dose date, day 1 will be the randomization date.

6.3 HANDLING OF MISSING VALUES

Missing data will be handled using a procedure specific to each variable and particular analysis as described in the sections relevant to each endpoint. If no method for missing data is discussed, descriptive analyses will be based upon observed data without imputation. [Appendix B](#) describes the general approaches to be used for missing data.

The algorithms for imputation of partial dates are applied based on following manner.

Adverse Event Onset

- If date is completely missing, date is set to date of first dose.
- If year is present and month and day are missing or year and day are present, and month is missing:
 - If year = year of first dose, then set month and day to month and day of first dose.
 - If year < year of first dose, then set month and day to December 31.
 - If year > year of first dose, then set month and day to January 1.
- If month and year are present and day is missing:
 - If year = year of first dose:
 - month = month of first dose, then set day to day of first dose date.
 - month < month of first dose, then set day to last day of month.
 - month > month of first dose, then set day to first day of month.
 - If year < year of first dose, then set day to last day of month.
 - If year > year of first dose, then set day to first day of month.
- For all other cases, set date to date of first dose.

Adverse Event End Date

-
- If year is present and month and day are missing or year and day are present and month is missing, set end month and day to December 31.
 - If month and year are present and day is missing, set the day to last day of the month.
 - If fatal event, date is set to minimum of imputed end date and death date.
 - For all other cases, set date to missing.

Concomitant Medication Start Date

- If start date is completely missing, start date is the date of informed consent except for the records that medication end date precedes date of informed consent.
- If start year is present and month and day are missing or year and day are present and month is missing, set start month and day to January 1.
- If start year and month are present and day is missing, set start day to 1st day of month.

Concomitant Medication End Date

- If end date is completely missing, end date is the last available date in the study.
- If end year is present and month and day are missing or year and day are present and month is missing, set end month and day to December 31.
- If end year and month are present and day is missing, set end day to last day of the month.

The imputed dates must be logical, ensuring that no end date is after database lock or death or before the start date.

